## **1 INTRODUCTION**

This statistical analysis plan (SAP) describes in detail the analyses and data presentation of all endpoints for the final clinical study report (CSR) of study AC-064A201.

This analysis plan is based on or refers to the following documents:

**Table 1      Associated Documents**

Two additional SAPs were developed for:

- Closed sessions of the independent data monitoring committee (IDMC) and Interim Safety Review (IR). This is based on this CSR SAP and is written by the Independent Statistical Analysis Center and is not reviewed by Actelion.
- Periodic reviews for Central Clinical Monitoring (CCM) and open sessions of the IDMC. This document describes specific and dedicated analyses as documented in the CCM Plan and refers mainly to this CSR SAP in terms of statistical methods and data presentation.

The source data for the analyses described in this SAP are the Study Data Tabulation Model (SDTM) datasets, provided by CDDM as Statistical Analysis System (SAS) datasets.

## **2 STUDY DESIGN AND FLOW**

Further details can be found in the protocol synopsis in [Appendix A](#).

## **2.1 Study design**

This is a prospective, multicenter, multinational, randomized, double-blind, placebo-controlled, two-part, dose-response Phase 1/2 study. This study is divided in two parts:

### Part A

Part A consists of four parallel treatment groups (including 0.5 mg, 1 mg, or 2 mg of ACT-334441 and placebo control). Approximately 48 subjects were randomized (1:1:1:1) via an interactive response technology (IRT) system to one of the four groups (i.e., 12 subjects in each group; three dose levels of 0.5 mg, 1 mg, or 2 mg ACT-334441, or placebo o.d.).

Subjects received ACT-334441 or placebo once daily (o.d.) for 12 weeks.

### Interim safety review

An Interim Review (IR) was conducted by the IDMC when all subjects enrolled into Part A completed Visit 4 (Week 4), unless prematurely discontinued. The IDMC evaluated the safety profile of ACT-334441 in systemic lupus erythematosus (SLE) subjects and gave a recommendation to continue the study as planned (i.e., proceed to Part B).

[figure not shown]
### Part B

Part B consists of two parallel treatment groups (including 4 mg ACT-334441 and placebo control).

Approximately 16 subjects were randomized (3:1) via an IRT system to one of the two groups (i.e., 12 subjects receiving 4 mg ACT-334441 and 4 subjects receiving placebo o.d.). Subjects enrolled in Part A were not eligible for Part B.

The study design is shown in [Figure 1](#).

**Figure 1** Study design of AC-064A201 investigating ACT-334441 in SLE subjects

EOT = End-of-Treatment; EOS = End-of-Study; FU = follow-up; IDMC= Independent Data Monitoring Committee.

## 2.2 Study visit and assessment schedule

See [Table 2](#) for a detailed plan of the visit and assessment schedule.

**Table 2** Visit and assessment schedule (same for part A and part B)

| Periods                                   | Name         | Pre-randomization | Treatment period   |               |          |          |  |                                       | FU                                     |  | Unscheduled                   |   |
|---|--------------|-------------------|--------------------|---------------|----------|----------|--|---------------------------------------|--|--|-------------------------------|---|
|   |              |                   | Duration           | Up to 30 days | 12 weeks |          |  |                                       | 16 weeks                               |  |                               | NA  |
| Visits                                    | Number       | 1                 | 2                  | 3             | 4        | 5        | 6  | 7                                     | 8                                      | 9                                      | U1, U2,...                    | I   |
|   | Name         | Screening         | Randomization (15) | W2            | W4       | W8       | EOT  | EOS                                   | Phone call FU                          | Unscheduled (17)                       | Re-initiation                 |   |
|   | Time         | Day -30 to -1     | Day 1              | Week 2        | Week 4   | Week 8   | Week 12 or earlier in case of premature discontinuation (16) | Last study treatment intake + 6 weeks | Last study treatment intake + 11 weeks | Last study treatment intake + 16 weeks | Any day between Day 1 and EOS | For study treatment interruptions that started up to Day 14 |
|   | Visit window |                   |                    | ± 3 days      | ± 5 days | ± 5 days | ± 5 days   | ± 5 days                              | ± 5 days                               | ± 5 days                               | NA                            |   |
| Informed consent*                         | X            |                   |                    |               |          |          |  |                                       |  |  |                               |   |
| Inclusion/exclusion criteria*             | X            | X                 |                    |               |          |          |  |                                       |  |  |                               |   |
| Demographics*                             | X            |                   |                    |               |          |          |  |                                       |  |  |                               |   |
| Medical history/smoking status*           | X            |                   |                    |               |          |          |  |                                       |  |  |                               |   |
| SLE history* (1)                          | X            |                   |                    |               |          |          |  |                                       |  |  |                               |   |
| Concomitant medications/SLE therapies*    | X            | X                 | X                  | X             | X        | X        | X  |                                       |  | X                                      | X                             |   |
| Physical examination* (2)                 | X            | X                 | X                  | X             | X        | X        | X  |                                       |  |  | X                             |   |
| Body weight and height* (3)               | X            |                   |                    |               |          |          | X  |                                       |  |  |                               |   |
| Disease activity scales*: SLEDAI-2K, PGA  | X            | X                 |                    | X             | X        | X        | X  |                                       |  | X                                      |                               |   |
| Quality of life questionnaire*: SF-36 v2™ |              | X                 |                    |               |          |          | X  |                                       |  |  |                               |   |
| Chest X-ray (4)                           | X            |                   |                    |               |          |          |  |                                       |  |  |                               |   |
| SBP/DBP* (5;6)                            | X            | X                 | X                  | X             | X        | X        | X  |                                       |  | X                                      | X                             |   |
| 12-lead ECG** (5)                         | X            | X                 | X                  | X             | X        | X        | X  |                                       |  | X                                      | X                             |   |
| ECG-Holter** (7)                          | X            | X                 |                    |               |          |          |  |                                       |  |  |                               |   |
| Echocardiography*                         | X            |                   |                    |               |          |          | X  |                                       |  |  |                               |   |
| Spirometry** (8)                          | X            |                   | X                  | X             | X        | X        | X  |                                       |  |  |                               |   |
| Ophthalmological examination*             | X            | .                 | X                  | X             | X        | X        | X  | X                                     |  |  |                               |   |

ACT-334441

Study AC-064A201

20 April 2017, page 15/125

Confidential

Statistical Analysis Plan

Doc D-17.230

| Periods  | Name         | Pre-randomization | Treatment period   |          |          |          |  |                                       | FU                                     |  | Unscheduled                   |   |
|--|--------------|-------------------|--------------------|----------|----------|----------|--|---------------------------------------|--|--|-------------------------------|---|
|  | Duration     | Up to 30 days     | 12 weeks           |          |          |          |  |                                       | 16 weeks                               |  | NA                            |   |
| Visits   | Number       | 1                 | 2                  | 3        | 4        | 5        | 6  | 7                                     | 8                                      | 9                                      | U1, U2,...                    | I   |
|  | Name         | Screening         | Randomization (15) | W2       | W4       | W8       | EOT  | EOS                                   | Phone call FU                          | Phone call FU                          | Unscheduled (17)              | Re-initiation   |
|  | Time         | Day -30 to -1     | Day 1              | Week 2   | Week 4   | Week 8   | Week 12 or earlier in case of premature discontinuation (16) | Last study treatment intake + 6 weeks | Last study treatment intake + 11 weeks | Last study treatment intake + 16 weeks | Any day between Day 1 and EOS | For study treatment interruptions that started up to Day 14 |
|  | Visit window |                   |                    | ± 3 days | ± 5 days | ± 5 days | ± 5 days   | ± 5 days                              | ± 5 days                               | ± 5 days                               | NA                            |   |
| OCT  |              | X                 |                    |          |          |          | X  |                                       |  |  |                               |   |
| Hematology (9)/ blood Chemistry**                  | X            | X                 | X                  | X        | X        | X        | X  |                                       |  |  | X                             |   |
| Pregnancy test */** (10)                           | X            | X                 | X                  | X        | X        | X        | X  | X                                     | X                                      | X                                      |                               |   |
| Viral serology / tuberculosis test**               | X            |                   |                    |          |          |          |  |                                       |  |  |                               |   |
| Additional serum sample for viral serology***      |              | X                 |                    |          |          |          |  |                                       |  |  |                               |   |
| ANA, anti-dsDNA antibodies, complement C3 and C4** | X            | X                 |                    | X        | X        | X        | X  |                                       |  |  | X                             |   |
| Exploratory biomarkers** (11)                      |              | X                 |                    | X        | X        | X        | X  |                                       |  |  |                               |   |
| Lymphocyte subsets*** (12)                         |              | X                 |                    |          |          |          | X  | X                                     |  |  |                               |   |
| Urine protein-to-creatinine ratio**                | X            | X                 |                    |          |          | X        |  |                                       |  |  | X                             |   |
| Urinalysis (dipstick)*                             | X            | X                 | X                  | X        | X        | X        | X  |                                       |  |  | X                             |   |
| PK sampling (pre dose)***                          |              |                   | X                  | X        | X        | X        | X  |                                       |  |  |                               |   |
| Study treatment dispensing & accountability* (13)  |              | X                 | X                  | X        | X        | X        |  |                                       |  |  |                               | X   |
| AEs* (14)  | X            | X                 | X                  | X        | X        | X        | X  |                                       |  |  | X                             | X   |
| SAEs* (14)   | X            | X                 | X                  | X        | X        | X        | X  | X                                     | X                                      | X                                      | X                             | X   |

\* Data collected in the eCRF

\*\* Electronically transferred to sponsor

\*\*\* Sample collection date recorded in the eCRF (for PK samples, time will also be recorded)

Assessments in part A and B are identical.

Day 1 (date of Randomization visit) is to be used as the reference date for the purpose of calculating the subsequent visit dates (and time windows).

For WOCBP, the serum pregnancy test at Visit 1 must be performed at least 3 weeks before the urine pregnancy test performed at Visit 2 prior to randomization.

The intervals between Visit 4 (Week 4), Visit 5 (Week 8) and Visit 6 (EOT) should not exceed 36 days.

- (1) History of positive ANA / anti-ds DNA antibodies will be included.
- (2) Complete physical examination (i.e., inspection, percussion, palpation and auscultation) will be performed at Visit 1 (Screening) and Visit 6 (EOT). A symptom-driven, abbreviated physical examination will be performed at all other visits in order to capture assessments needed for the SLEDAI-2K
- (3) Height only at Screening.
- (4) A chest X-ray that has been performed within 3 months prior to Screening can be used (in this case, no need to repeat chest X-ray at Screening).
- (5) On Day 1 and at re-initiation, SBP/DBP assessment and 12-lead ECG will be done pre-dose and hourly until 6 h post-dose; after 6 h, subjects may be discharged from the hospital if they meet the discharge criteria, otherwise SBP/DBP assessments and 12-lead ECG will be performed hourly until discharge criteria are met. If discharge criteria are not met after 12 h, the subject must be permanently discontinued. At all other visits, only pre-dose SBP/DBP assessments and 12-lead ECG will be performed.
- (6) At Screening, SBP/DBP will be assessed in supine position and after 1 to 3 minutes in standing position to assess orthostatic hypotension. At all other visits, SBP/DBP will be assessed in supine position.
- (7) At Screening, 24 hour ECG-Holter will start before 12:00. On Day 1, 24 hour ECG-Holter will start immediately before dosing.
- (8) Two spirometry assessments will be performed at Visit 1 (Screening). The assessments should be at least 5 days apart. The last assessment will count as baseline.
- (9) Hematology assessments including coagulation tests will be performed at each visits until EOS
- (10) Serum pregnancy tests will be performed at Screening and EOS. Urine pregnancy tests will be performed at all other visits (including telephone calls FU, 11 weeks and 16 weeks after study treatment discontinuation).
- (11) IgM, IgG, IgA, CRP, fibrinogen, and BLyS will be measured in serum. At Randomization visit only, anti-Smith, anti-cardiolipin, and anti-ribosomal P will also be measured. EDTA plasma samples will be shipped via central laboratory to Actelion for analysis of CXCL10 and other soluble biomarkers potentially related to SLE and/or S1P1 modulation.
- (12) Blood samples will be shipped via central laboratory to Actelion for lymphocyte subsets analysis.
- (13) No study drug dispensing at V3 and re-initiation visit
- (14) All AEs and SAEs that occur after signing the Informed Consent Form and up to 6 weeks (AEs) or 16 weeks (SAEs) after study treatment discontinuation must be reported.
- (15) Prior to randomization, the following central laboratory results must be available to confirm eligibility: ANA, anti-dsDNA, Hepatitis B surface antigen, Hepatitis C, HIV1 and HIV2, varicella-zoster virus, urine protein-to-creatinine ratio, ALT/AST/TBL, pregnancy test (if applicable).
- (16) EOT visit should preferably take place 1 day after last study treatment dose, and no later than 7 days.
- (17) Unscheduled visits may be performed at any time during the study. Recording of changes in concomitant medications and background SLE therapies since last visit needs to be performed at each unscheduled visit. Further assessments including 12-lead ECG, SBP/DBP, SLEDAI-2K, PGA, laboratory assessments for SLEDAI-2K scoring (i.e., hematology/blood biochemistry, urinalysis, anti-dsDNA, complement C3 and C4) may be performed at the discretion of the investigator.

AE = adverse event; ALT = alanine aminotransferase; ANA = anti-nuclear antibodies; anti-dsDNA = anti-double-stranded DNA; AST = aspartate aminotransferase; BLyS = B lymphocyte stimulator; CRP = C-reactive protein; CXCL10 = C-X-C motif chemokine 10; ECG = electrocardiogram; eCRF = electronic Case Report Form; EDTA= ethylenediaminetetraacetic acid; DBP = diastolic blood pressure; EOS = End-of-Study; EOT = End-of-Treatment; FU = follow-up; HIV = human immunodeficiency virus; NA = not applicable; OCT = optical coherence tomography; PGA = Physician's Global Assessment; PK = pharmacokinetic; SAE = serious adverse event; S1P1 = sphingosine-1-phosphate receptor 1; SBP = systolic blood pressure; SF-36 = Short-Form 36; SLE = systemic lupus erythematosus; SLEDAI-2K = Systemic Lupus Erythematosus Disease Activity Index-2000; TBL = total bilirubin; WOCBP = women of childbearing potential.

### 3 OBJECTIVES

#### 3.1 Main objective(s)

- To investigate the pharmacodynamics (PD) of ACT-334441 in adult subjects with SLE.
- To investigate the safety and tolerability of ACT-334441 in adult subjects with SLE.

#### 3.2 Exploratory objectives

- To investigate the pharmacokinetics (PK) of ACT-334441 in adult subjects with SLE.
- To investigate the effect of ACT-334441 treatment on disease activity in adult subjects with SLE.

### 4 CHANGES OR CLARIFICATIONS TO ANALYSES PLANNED IN THE STUDY PROTOCOL

#### 4.1 Changes to the analyses planned in the study protocol

##### 4.1.1 Pharmacodynamic analysis set definition

Previously Read

The pharmacodynamics analysis set (PDS) includes all subjects who received at least 3 weeks of study treatment and have at least one lymphocyte count measurement between the Week 4 visit and Week 12 visit.

Now Reads:

The pharmacodynamics analysis set (PDS) includes all subjects who received at least 21 days of uninterrupted study treatment, with lymphocyte count measurements at baseline and post-baseline (namely, one sample taken at least 21 days after the first study treatment intake and no later than 7 days after the last study treatment intake and no study treatment interruption documented in the first 21 days).

Rationale for change:

To allow analysis of the primary endpoint, the change from baseline to end of treatment (EOT) in lymphocyte count, based on a value at baseline and a value 'under treatment' so that the expected drug dependent effect on the lymphocyte count is biologically meaningful and has sufficient time to reach the full effect on lymphocyte reduction.

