### **5.1.8 Study treatment interruptions**

Study treatment should not be interrupted. If study treatment intake is interrupted by the subject for a day or more for any reason, she/he must immediately inform the principal investigator / treating physician. If a subject forgets to take study treatment in the morning, she/he should take it on the same day and resume regular dosing the next morning.

The following guidance is provided for re-initiation of study treatment after study treatment interruptions.

Note that under no circumstances should a subject take more than one capsule per day.

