### 11.2.2 PD Analysis Set

The Pharmacodynamics Analysis Set (PDS) includes all subjects who received at least 3 weeks of study treatment and have at least one lymphocyte count measurement between the Week 4 visit and Week 12 visit. Subjects will be analyzed according to the treatment they received.

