### 11.6 Sample size

#### 11.6.1 Sample size justification

[figure not shown]
The sample size for the study was determined based on simulations. A sample size of 64 subjects (12 in each ACT-334441 dose group of 0.5 mg, 1 mg, 2 mg, 4 mg and 16 in the placebo group) would provide an average power of at least 90% to show a significant dose-response relationship at a one-sided alpha significance level of 5%, under the assumption of a lymphocyte % reduction compared to baseline of 0% (mean at Week 12 =  $2.0 \times 10^9/L$ ) for placebo and a maximum of 70% for any ACT-334441 dose (mean at Week 12 =  $0.6 \times 10^9/L$ ). A maximum lymphocyte % reduction compared to baseline of 70% was assumed based on results obtained in Phase 1 with ACT-334441 and with other S1P modulators. The pooled standard deviation is assumed to be  $0.45 \times 10^9/L$ . This takes into account 10% of subjects being excluded from the PDS.

If Part B is not conducted and the 4 mg dose is not tested then there will be an average power of at least 80% to show a significant dose-response relationship with three doses at a one-sided significance level of 5%, using the same assumptions as above (based on a total sample size of 48 subjects [12, 12, 12 and 12 in placebo, 0.5 mg, 1 mg and 2 mg, respectively]).

Assuming a % reduction in lymphocyte counts of between 25% to 70% (and pooled standard deviation =  $0.45 \times 10^9/L$ ) compared to placebo, any single pairwise dose comparison will have between 77% and 100% power to detect a difference at a 2-sided significance level of 5%.

Assumptions on the placebo response rate, maximum effect sizes and candidate dose-response models are based on the observed lymphocyte counts in study AC-064-101.

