### 5.5.1 Main pharmacodynamic variable

The main variable is the change in lymphocyte count in peripheral blood from baseline to EOT, defined as:

- Total lymphocyte count at EOT – total lymphocyte count at baseline

The value at baseline is defined as the last non-missing value obtained from a sample taken prior to the first study treatment intake.

The value at EOT is defined last post-baseline value from a sample taken at least 21 days after the first study treatment intake (with no interruptions) and no later than 7 days after the last study treatment intake for the analyses on the PDS and on the PPS.

The value at EOT is defined as the last post-baseline value up to Week 12 for the analyses on the FAS (application of the intention-to-treat principle [ITT] utilizing the Last observation carried forward [LOCF] technique for missing data).

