### **Additional expressions**

#### **End of treatment (EOT)**

For analyses ran on the FAS or the SAF, an additional observation (AVISITN = 6.1, AVISIT = 'End-of-treatment', DTTYPE = 'LOCF') is created for all subjects with at least one post-baseline assessment available. It is populated with the latest non-missing value assigned from analysis visit Week 2 to analysis visit Week 12 according to the LOCF principle.

In addition, for analyses ran on the PDS or the PPS, an extra observation (AVISITN = 6.2, AVISIT = 'End-of-treatment', DTTYPE = 'LOCF') is created for all subjects with at least one non-missing post-baseline assessment performed at least 21 days after the first study treatment intake but no later than 7 days after the last study treatment intake. It is populated with the latest value available fitting these criteria.

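### The PDS rule on interruptions in the first 21 days removes subjects who restart and are then dosed for well over 21 days before the EOT sample, against the rule's own rationale; the EOT value definition in SAP 5.5.1 adds an open-ended no-interruption phrase

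*SAP*

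**What the plan says.** Protocol 11.2.2 defined the PDS without any condition on interruptions: "all subjects who received at least 3 weeks of study treatment and have at least one lymphocyte count measurement" in the Week 4 to Week 12 range. SAP 4.1.1 openly replaces this. The subject must have "received at least 21 days of uninterrupted study treatment", and the qualifying sample must be taken "no later than 7 days after the last study treatment intake and no study treatment interruption documented in the first 21 days". The reason given is that the value should be taken on treatment and late enough for the lymphocyte effect to be complete.

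SAP 7.1.5.1 and the population flag in SAP 11.2.2 apply the same exclusion (21 days in one, 3 weeks in the other). SAP 4.1.2 and 7.1.3 state that a subject outside the PDS is also outside the PPS, on the ground that the pharmacodynamic effect would be insufficient.

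Two further places define the EOT value itself:

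- SAP 5.5.1, for the PDS and PPS, takes the last value "from a sample taken at least 21 days after the first study treatment intake (with no interruptions"; the bracket closes there, with no time limit on the phrase.
- SAP 11.1.1, End of treatment (EOT), creates the record when a subject has "at least one non-missing post-baseline assessment performed at least 21 days after the first study treatment intake but no later than 7 days", the 7 days being counted from last intake. It has no interruption condition.

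The protocol foresees interruptions. Section 5.1.8 opens the guidance with "If study treatment intake is interrupted by the subject for a day or more for any reason". Section 5.1.8.1 provides one re-initiation, within 7 days of the first missed dose, when the gap starts on Days 1–14. Under 5.1.8.2, dosing continues after Day 14 through gaps shorter than 7 days.

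**The concern.** The rationale needs enough uninterrupted dosing before the sample that supplies the EOT value. The rule instead looks at a fixed calendar window at the start of treatment. The two agree only when the sample is taken soon after Day 21. For a Week 12 sample, a gap in the first three weeks says almost nothing about whether the effect is complete.

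The consequence is that randomised, treated and evaluable subjects leave the main MCP-Mod test, the pairwise comparisons and the PPS because of an event after randomisation. SAP 5.3.4 shows that this event can be an interruption for an adverse event, so exclusions need not be balanced across arms of 12. The PPS argument of insufficient effect does not describe a subject with nine or more weeks of dosing after restart.

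Separately, the endpoint value should have one derivation. Take a subject whose only gap is after Day 21. SAP 5.5.1 read literally points to an earlier sample or to none, while SAP 11.1.1 takes the latest sample in the window.

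**Working it through.** **1. The plan's own power figure (Protocol 11.6.1).** A 25% reduction from 2.0 is 0.5 × 10⁹/L, with SD 0.45. For 12 vs 12, SE = 0.45 × √(1/12 + 1/12) = 0.184, z = 0.5/0.184 = 2.72, and power = Φ(2.72 − 1.96) = 77.7%. This reproduces the stated 77%. With 16 placebo subjects and 10% loss from the PDS (14.4 vs 10.8), SE = 0.181, z = 2.76 and power is 78.8%.

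**2. Dosing after restart.** The treatment period is 84 days (12 weeks). Days dosed after restart = 84 − restart day + 1.

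- First miss Day 2, restart Day 3: 82 days.
- First miss Day 8, restart Day 15: 70 days.
- First miss Day 14, restart Day 21 (the latest allowed): 64 days.

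The rule also catches gaps starting on Days 15–21. A six-day gap from Day 21, with dosing resumed on Day 27, leaves 84 − 27 + 1 = 58 days.

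The benchmarks are a lymphocyte plateau at 20–23 days (SAP 10.6.2) and steady state at 20–32 days (Protocol 1.3.2.1). Every case exceeds both, and every case is excluded.

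**3. Concentration at the EOT sample.** Assume one-compartment superposition of daily doses: C(85) = Σ exp[−k(85 − d)] over dosed days d from 1 to 84. Here k = ln 2 / t½, and t½ is 12 to 22 days (Protocol 1.3.2.1, after repeated dosing). Results relative to no interruption:

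| Missed doses | t½ 12 days | t½ 22 days | PDS |
|---|---|---|---|
| Day 10 only | 99.9% | 99.7% | excluded |
| Days 10–15 | 99.5% | 97.9% | excluded |
| Days 14–20 (latest restart) | 99.2% | 97.2% | excluded |

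**4. What the exclusions could cost.** The documents give no interruption rate, so the losses below are assumptions. Pairwise power at a 25% reduction (normal approximation, 16:12 allocation) is 78.8% at 10% PDS loss, 74.0% at 20% and 68.2% at 30%. A simulation of the maximum-contrast test used the five SAP shapes, a maximum effect of 1.4 × 10⁹/L, SD 0.45 and one-sided 5% (critical value about 1.85). Power stayed at about 100% up to 40% loss.

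**5. Wordings side by side.** SAP 4.1.1, 7.1.5.1 and 11.2.2 agree in effect on interruptions. SAP 5.5.1 has no time limit. SAP 11.1.1 has no interruption condition, although the PDS flag has already filtered early interruptions before that record is used.

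**The case against.** Several points on the other side stand. The departure from the protocol is declared with reasons, so the protocol text is not a competing version. Three of the SAP wordings are one rule. The bracket in SAP 5.5.1 directly follows the 21 days and can be read as qualifying only them. For a subject whose only usable sample is near Week 4, the existing rule does what its rationale asks. SAP 10.6.4 repeats MCP-Mod and ANCOVA on the FAS, which keeps every randomised subject.

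The FAS repeat does not replace a sound PDS rule. By SAP 10.6.2 it carries forward the last post-baseline value with no time restriction, so it also admits values taken before the plateau.

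A reader might infer two stronger points that the documents do not support.

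- *That the rule wrongly keeps subjects with a gap just before the EOT sample.* In the same model, missing Days 78–83 leaves 72% to 82% of the Day 85 concentration. A fully adherent subject sampled on Day 91, inside the accepted 7-day window, has 2^(−6/12) = 71% to 2^(−6/22) = 83%. The plan already accepts that drop for everyone. Concentration is also not the endpoint: Protocol 1.3.2.2 reports 28 days for mean counts at 4 mg to return to the normal range.
- *That the rule will use up the planned allowance* ("This takes into account 10% of subjects being excluded from the PDS"). No missed-dose rate is given. SAP 5.3.4 counts an interruption only when the drug log records a temporary one, the Day 1 dose is taken on site, and a forgotten morning dose is to be taken later the same day. Any assumed exclusion percentage would be guesswork.

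**Conclusion.** The concern holds in a limited form. The first-21-day rule excludes from the main analysis and the PPS subjects with 64 to 82 days of dosing after re-initiation, and about 97% to 99.9% of the uninterrupted concentration at Day 85. That contradicts the rule's stated purpose. The day counts follow from the protocol and assume completion of 84 days. The concentrations rest on a one-compartment model and the Phase 1 half-life range in healthy subjects.

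The no-interruption phrase in SAP 5.5.1 is a smaller, separate defect: it is ambiguous, and read literally it conflicts with SAP 11.1.1.

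The number of affected subjects and any imbalance between arms are unknown, so no bias in the result is shown. Main MCP-Mod power is not threatened. Pairwise power at the smallest planned effect would fall only if losses rose well beyond 10%. The change is worth making before unblinding because it is cheap and reduces avoidable post-randomisation exclusions.

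**What to change.** Use one definition in SAP 4.1.1, 5.5.1, 7.1.5.1, 11.1.1 and 11.2.2:

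- The EOT value for the PDS and PPS is the last central-laboratory value taken no more than 7 days after last intake and at least 21 days after first intake. If an interruption is documented in the first 21 days, the 21 days run from resumption of dosing.
- A subject is in the PDS if a baseline value and such an EOT value exist.
- Delete the open-ended bracket in SAP 5.5.1 and the blanket exclusion for an interruption in the first 21 days.
- Tabulate reasons for PDS exclusion by arm. SAP 10.3.3 already counts exclusions by arm and lists reasons, but tabulates reasons only for the PPS.

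This keeps the protection for early samples. With restart on Day 15, a Week 4 sample on Day 29 is 14 days after restart and does not qualify; a Week 8 sample on Day 57 is 42 days after and does.

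A wider rule, counting from the last interruption at any time, is not recommended. One missed dose on Day 75 would discard a Week 12 value taken at about 97% of the uninterrupted concentration.

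The cost is SAP wording and one derivation from the study drug log. A few re-initiated subjects with slightly lower total exposure (77 to 83 of 84 days in the re-initiation cases) would enter the PDS. No dosing or re-initiation rule changes.
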